## 6. ANALYSIS PRINCIPLES

Primary outcome measure is the OI at day 7. Unadjusted (primary analysis) and adjusted analysis will be carried out to test whether there is a statistically significant difference between the aspirin & placebo groups. Secondary analysis will be carried out, if the day 7 OI values are missing, using last value carry forward method.

Secondary outcome measures are OI, CRs, PF ratio, and SOFA score at day 4, 7, 14 and safety. Unadjusted and adjusted analysis will be carried out on OI, CRs, PF ratio, SOFA score, to test whether there is a statistically significant difference between the groups.

Unadjusted analysis will be carried out using Independent sample t-test. Adjusted analysis will be carried out using ANCOVA or [mixed modelling technique](#), based the number of data points available at each time point. Estimates & 95% confidence interval will be reported.

The number of AE, ARs, SAE, SARs, SUSARs and number (%) of patient experiencing the events will be reported. Fisher's exact test and proportion test will be used to check whether incidences of adverse events differ between the groups. Relative risk and 95% CI will be reported.

Exploratory analysis on mediators will be carried out using student t-tests or non-parametric alternative and Fishers Exact Test, presented by day where applicable. The estimates & 95% CIs will be reported. Statistical diagnostic methods will be used to check for violations of the assumptions, and transformations will be performed if required. For binary outcome measures, risk ratios and associated 95% CI will be calculated. Survival analysis technique will be used for time-to-event data. Median survival time & 95% CI will be estimated using Kaplan-Meier estimation method and the Kaplan-Meier plots will be presented. In all time-to-event analyses, patients that did not experience the event in question (e.g. death) were censored on the date last seen or 90 days. The equality of survivorship function of aspirin & placebo group will be tested

for significance using a log-rank  $\chi^2$  test. Hazard ratios (HRs) & 95% CIs will be reported if the proportionality assumption holds.

Correlations between changes in the biological markers measured and physiological and clinical outcomes will be assessed by appropriate graphical and statistical methods including Pearson's (or Spearman's) correlation coefficient.

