A secondary analysis excluding patients identified to have aspirin resistance will also be undertaken.

Analyses will be conducted according to intention to treat principle. All statistical tests will be 2-sided and a p-value of 0.05 will be considered as statistically significant, unless adjustment for multiple testing was needed. A single analysis is planned at the end of the trial. Every effort will be made to minimise missing baseline and outcome data in this trial. Any ad-hoc analysis will be reported as per the regulatory requirement.

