Lowest eGFR mL/min									
	Aspirin	n	xx.x ± x.x	n	xx.x ± x.x	n	xx.x ± x.x	n	xx.x ± x.x
	Placebo	n	xx.x ± x.x	n	xx.x ± x.x	n	xx.x ± x.x	n	xx.x ± x.x
	p-value #			0.xxx		0.xxx		0.xxx	

# p values for ANCOVA or mixed model

**Table A 2.. Adverse events/reactions (AE/AR), serious adverse events/reactions (SAE/SAR) & suspected unexpected serious adverse reactions**

		Number of Events			Number of Patients				
		Total	Aspirin	Placebo	Total N=<n>	Aspirin N=<n>	Placebo N=<n>	RR (95%I)	p-values
AE/AR, SAE/SAR and SUSAR	Total number of adverse events (AEs)	n	n	n	n (%)	n (%)	n (%)	x.xx (x.xx to x.xx)	x.xx
	Total number of adverse reactions (ARs)	n	n	n	n (%)	n (%)	n (%)	x.xx (x.xx to x.xx)	x.xx
	Total number of serious adverse events (SAEs)	n	n	n	n (%)	n (%)	n (%)	x.xx (x.xx to x.xx)	x.xx
	Total number of serious adverse reactions (SARs)	n	n	n	n (%)	n (%)	n (%)	x.xx (x.xx to x.xx)	x.xx
	Total number of events related to study drug and unexpected (SUSAR)	n	n	n	n (%)	n (%)	n (%)	x.xx (x.xx to x.xx)	x.xx
AEs	Blood and lymphatic system disorders	n	n	n	n (%)	n (%)	n (%)	x.xx (x.xx to x.xx)	x.xx
	Cardiac disorders	n	n	n	n (%)	n (%)	n (%)	x.xx (x.xx to x.xx)	x.xx
	Gastrointestinal disorders	n	n	n	n (%)	n (%)	n (%)	x.xx (x.xx to x.xx)	x.xx
	Hepatobiliary disorders	n	n	n	n (%)	n (%)	n (%)	x.xx (x.xx to x.xx)	x.xx
	General disorders and administration site conditions	n	n	n	n (%)	n (%)	n (%)	x.xx (x.xx to x.xx)	x.xx
	Infections and infestations	n	n	n	n (%)	n (%)	n (%)	x.xx (x.xx to x.xx)	x.xx
	Injury, poisoning and procedural complications	n	n	n	n (%)	n (%)	n (%)	x.xx (x.xx to x.xx)	x.xx
	Musculoskeletal and connective tissue disorders/Elevated Creatinine Kinase	n	n	n	n (%)	n (%)	n (%)	x.xx (x.xx to x.xx)	x.xx
	Investigations	n	n	n	n (%)	n (%)	n (%)	x.xx (x.xx to x.xx)	x.xx
	Nervous system disorders	n	n	n	n (%)	n (%)	n (%)	x.xx (x.xx to x.xx)	x.xx
	Renal and urinary disorders	n	n	n	n (%)	n (%)	n (%)	x.xx (x.xx to x.xx)	x.xx
	Respiratory, thoracic and mediastinal disorders	n	n	n	n (%)	n (%)	n (%)	x.xx (x.xx to x.xx)	x.xx
Skin and subcutaneous tissue disorders	n	n	n	n (%)	n (%)	n (%)	x.xx (x.xx to x.xx)	x.xx	
SAEs	Blood and lymphatic system disorders	n	n	n	n (%)	n (%)	n (%)	x.xx (x.xx to x.xx)	x.xx
	Cardiac disorders	n	n	n	n (%)	n (%)	n (%)	x.xx (x.xx to x.xx)	x.xx
	Gastrointestinal disorders	n	n	n	n (%)	n (%)	n (%)	x.xx (x.xx to x.xx)	x.xx
	Hepatobiliary disorders	n	n	n	n (%)	n (%)	n (%)	x.xx (x.xx to x.xx)	x.xx

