**Table A 3. Age & Kidney Function**

Status	All patients	Treatment Group		T-test p-values
		Aspirin	Placebo	
Number (%) of patients Age>65	n (xx.x%)	n (xx.x%)	n (xx.x%)	0.xxx
Number (%) of patients aged > 65 starting RRT after randomisation	n	n	n	0.xxx
Baseline				
EGFR *	xx.x ±xx.x	xx.x ±xx.x	xx.x ±xx.x	0.xxx
Creatinine	xx.x ±xx.x	xx.x ±xx.x	xx.x ±xx.x	0.xxx
Change from baseline to day 7				
EGFR *	xx.x ±xx.x	xx.x ±xx.x	xx.x ±xx.x	0.xxx
Creatinine	xx.x ±xx.x	xx.x ±xx.x	xx.x ±xx.x	0.xxx

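### Day-7 creatinine is tested only by a t-test on change, and day-7 eGFR by two methods with no lead named; a single baseline-adjusted ANCOVA would be a free, modest gain in precision

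*SAP*

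**What the plan says.** Two table shells in Appendix 1 of the SAP deal with kidney function.

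- **Age & Kidney Function table.** It is labelled Table A 3, a number that the main clinical outcomes table also carries, so it is called the kidney table below. Its only p-value column is headed "T-test p-values". Its last block, "Change from baseline to day 7", has one row for eGFR and one for creatinine. The eGFR label carries an asterisk that the available text does not explain.
- **Table A7 (clinical laboratory assessments).** It has a row "Lowest eGFR mL/min" with p-values at days 4, 7 and 14, footnoted "p values for ANCOVA or mixed model". Creatinine has no row in Table A7 or in any table other than the kidney table.

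Section 6 states the general scheme: "Unadjusted analysis will be carried out using Independent sample t-test", and "Adjusted analysis will be carried out using ANCOVA or" a mixed model. For the secondary outcomes it limits this pair by name: "Unadjusted and adjusted analysis will be carried out on OI, CRs, PF ratio, SOFA score". Neither eGFR nor creatinine is mentioned there. Section 6 also sets the threshold: "All statistical tests will be 2-sided and a p-value of 0.05 will be considered as statistically significant", subject to any multiplicity adjustment found necessary. No covariates are named anywhere. The mixed-model shell in Table A4, whose title includes laboratory variables, lists only group, day and their interaction.

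**The concern.** There are two linked issues.

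First, day-7 eGFR appears to be tested twice, by methods that can give different answers, and nothing says which result represents renal function. A reader who gives weight to whichever p-value is significant is working at an error rate somewhat above 5%.

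Second, creatinine is assessed only by the t-test on change. That test subtracts the whole baseline value, which amounts to fixing the baseline slope at 1. If the true slope is below 1, part of any chance baseline difference between arms carries over into the comparison with its sign reversed, and precision is lost. ANCOVA estimates the slope from baseline values that the kidney table already requires.

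What is at stake is some sensitivity to a renal difference in a trial of about 30 per arm, and clarity about which eGFR result is to be read.

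**Working it through.** **Inputs.** From the SAP: 28 evaluable per arm (Section 5) and two-sided 0.05 (Section 6). Assumed: a baseline to day-7 correlation ρ of 0.3 to 0.9, because the SAP gives none.

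**The plan's own figure.** The SAP gives no precision or power figure for eGFR or creatinine. Its primary-outcome sample size reproduces: a difference of 39 with SD 51 needs 27.84 per arm by the exact t-test, so 28, with power 80.2%. Allowing 5% dropout, 56/0.95 = 58.9, so 59 against the stated 60. This only confirms 28 per arm as a reasonable size for the check below.

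**Variance.** Let σ² be the variance at both times.

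- Change score: 2σ²(1 − ρ)
- ANCOVA residual: σ²(1 − ρ²) = σ²(1 − ρ)(1 + ρ)
- Ratio, change score to ANCOVA: 2/(1 + ρ)

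| ρ | Change (σ² = 1) | ANCOVA (σ² = 1) | Variance ratio | SE ratio |
|---|---|---|---|---|
| 0.3 | 1.40 | 0.91 | 1.54 | 1.24 |
| 0.5 | 1.00 | 0.75 | 1.33 | 1.15 |
| 0.7 | 0.60 | 0.51 | 1.18 | 1.08 |
| 0.9 | 0.20 | 0.19 | 1.05 | 1.03 |

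These ratios do not depend on the number per arm. The direction does not need equal variances. With SDs σ₀ at baseline and σ₇ at day 7, the change-score variance minus the ANCOVA variance is (σ₀² + σ₇² − 2ρσ₀σ₇) − σ₇²(1 − ρ²) = (σ₀ − ρσ₇)², which is never negative.

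**Illustration at 28 per arm.** There were 20,000 simulated trials per setting, with normal data. The true effect was set at 2.8 × √((1 − ρ²) × 2/28) SD, so that ANCOVA has about 78% power. That effect was chosen for the comparison and has no basis in the SAP.

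| ρ | Power, change t-test | Power, ANCOVA | Opposite sides of 0.05, true effect | Opposite sides of 0.05, no effect | Either significant, no effect |
|---|---|---|---|---|---|
| 0.3 | 60% | 77% | 23% | 5.6% | 8.0% |
| 0.5 | 67% | 78% | 17% | 4.4% | 7.0% |
| 0.7 | 72% | 78% | 12% | 3.7% | 6.8% |
| 0.9 | 77% | 78% | 6% | 1.8% | 5.7% |

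With no effect, each test taken alone rejected in 4.7% to 5.2% of trials, so each keeps its nominal level.

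**Why the mixed-model option matters.** Suppose baseline is one of the Day levels, as the terms in Table A4 would allow. With complete data, the day-7 Group*Day contrast is (aspirin day 7 − aspirin baseline) − (placebo day 7 − placebo baseline), in arm means. That is the difference in mean change, the same estimate that the kidney table's t-test uses, so it brings no gain in precision. The ratios above therefore compare the change-score test with a baseline-adjusted ANCOVA. They do not compare it with whatever Table A7 turns out to contain.

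**The case against.** The case for leaving the plan alone has several parts.

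- **Status of the measures.** The SAP's safety outcome is adverse events and reactions (Sections 2.2 and 7.5), analysed by Fisher's exact test, a proportion test and relative risk. Renal and urinary disorders have their own rows in the adverse-event table. eGFR and creatinine are in no outcome list. This stands. A reader might infer that a declared safety outcome has two competing p-values, and the SAP does not support that.
- **Draft shells.** The appendix is presented as example draft tables. The t-test heading also sits above count rows for age and renal replacement, so it may be a loose label. This lowers the weight of the point, but the shell is the only statement of how creatinine will be tested.
- **Same eGFR?** One table specifies the lowest value and the other an asterisked eGFR. That they are the same quantity is likely but not stated.
- **Validity.** A reader might infer that the change-score test is biased. It is not: under randomisation it is unbiased on average. The loss is one of precision and of sensitivity to chance imbalance.
- **Table A7 as the better test.** A reader might infer that Table A7 is already the more precise analysis. Without named covariates that cannot be said.
- **Selective reporting.** Both p-values sit in planned tables, so both would be expected in the report. What remains is that neither is named as leading.
- **Section 6.** The t-test could be read as the unadjusted half of the Section 6 pair. That is only an analogy: Section 6 names four other outcomes, and the kidney table tests a change, not the day-7 value.

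**Conclusion.** The point holds as a free improvement of minor severity. Creatinine's only planned test is a t-test on change. For day-7 eGFR the SAP plans that test and an ANCOVA or mixed model, without naming the lead.

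Against ANCOVA with baseline as covariate, the t-test on change has 1.54 to 1.05 times the variance for an assumed correlation of 0.3 to 0.9. The gain is worth having at low or moderate correlation and slight at 0.9. The ratios assume equal variances at the two times, and the choice of ρ is not informed by the SAP. The simulated powers rest on an effect size chosen for illustration and are not a demonstrated loss in this trial.

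The documents do not support a claim that renal safety is wrongly tested or that the safety conclusion is compromised. The primary outcome, the sample size and the adverse-event analysis are unaffected.

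**What to change.** 1. Name one analysis for both day-7 eGFR and day-7 creatinine: ANCOVA of the day-7 value on arm, with the baseline value of the same variable as covariate. Report the adjusted difference with 95% CI. Table A7 is the natural place, with a creatinine row added for day 7.
2. In the kidney table, keep the mean change to day 7 for both variables as description and drop its p-value.
3. State whether the asterisked eGFR in the kidney table is the same quantity as the lowest eGFR in Table A7.
4. If a mixed model is used instead, state that baseline enters as a covariate and not as a level of Day, and that the day-7 arm difference is the estimate to be read.

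The cost is SAP wording and two table shells, ideally settled before unblinding. No new data are needed, since the kidney table already requires baseline and day-7 values of both variables.

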**Table A 6. Survival data and length of ventilation and stay data**

	Aspirin	Placebo	p value
Ventilator free days (days)	n; xx.x ± x.x	n; xx.x ± x.x	0.xxx
Duration of ventilation (days)			
All patients	n; xx.x ± x.x	n; xx.x ± x.x	0.xxx
ICU survivors	n; xx.x ± x.x	n; xx.x ± x.x	0.xxx
ICU non-survivors	n; xx.x ± x.x	n; xx.x ± x.x	0.xxx
Duration of ICU stay (days)			
All patients	n; xx.x ± x.x	n; xx.x ± x.x	0.xxx
ICU survivors	n; xx.x ± x.x	n; xx.x ± x.x	0.xxx
ICU non-survivors	n; xx.x ± x.x	n; xx.x ± x.x	0.xxx
Duration of hospital stay (days)			
All patients	n; xx.x ± x.x	n; xx.x ± x.x	0.xxx
ICU survivors	n; xx.x ± x.x	n; xx.x ± x.x	0.xxx
ICU non-survivors	n; xx.x ± x.x	n; xx.x ± x.x	0.xxx
All-cause mortality 28 days post randomisation	n (xx.x%)	n (xx.x%)	0.xxx
All-cause mortality 90 days post randomisation	n (xx.x%)	n (xx.x%)	0.xxx

Mean ± SD & n (%) presented for treatment arms
